3.3 Current Standard of Care

A recent international symposium generated guidelines for weaning from MV. These guidelines state that active weaning from MV should commence when the pathology responsible for the institution of MV has been resolved and when the patients are clinically stable.¹³ A weaning trial commonly consists of a period of completely unsupported breathing (e.g., T-tube trial) or a period of minimal ventilator support (e.g., pressure support ventilation). If the patient does well during the weaning trial (i.e. is able to comfortably breathe unassisted) he/she is extubated; otherwise, the patient resumes MV.¹³

When patients do not pass the first weaning trial, the potential mechanisms for weaning failure must be identified and addressed.¹³ In addition, the aforementioned guidelines suggest implementing daily SBTs, during which the work of breathing accomplished by the ventilator is progressively reduced, and thus, the respiratory muscles weakened during the preceding pre-weaning period of MV are reconditioned.^{9,15}

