Each participant will receive either active or placebo electrical muscle stimulation to the abdominal wall during exhalation for sixty minutes per day, five days per week for the shorter of six weeks or until the patient is weaned from mechanical ventilation. Participants will be assigned to active or placebo stimulation in random order (using a random number generator). Evaluations will be performed at baseline, after three weeks of treatment and at the end of treatment. A flow diagram of the study protocol is shown in Figure 3

[figure not shown]

Figure 3 Study Flow Diagram

The maximum duration of participant participation is 45 days. The total duration of the study is expected to be 6 months.

7 Outcome Measures

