7.2 Secondary Outcome Measures

The secondary outcome measures in this study are:

- **Thickness of the Abdominal Wall Muscles** – The end inspiratory and end expiratory thickness of the external oblique, internal oblique and transversus abdominis muscles will be measured using ultrasound.
- **Thickness of the Diaphragm** - The end inspiratory and end expiratory thickness of the diaphragm will be measured using ultrasound.
- **Weaning Success** – Defined as 72 hours of spontaneous respiration without any mechanical ventilation support.
- **Number of Days Taken to Wean** – Defined as the time from the patient's original admission to the point of weaning success.
- **Time spent breathing without mechanical ventilation support** - The time spent breathing without MV support will be recorded on a daily basis throughout the study.
- **Cough Peak Flow** – The peak flow during a voluntary cough will be recorded.
- **Resting Breathing** – This outcome will be assessed using measurements of tidal volume, respiratory rate and minute ventilation during a one-minute period of resting breathing.
- **Adherence to the Weaning Protocol** – The number and duration of the weaning sessions supported by electrical stimulation during the study period will be recorded for each participant.
- **Sensation of Stimulation Experienced by the Patient** – Surface electrical muscle stimulation stimulates sensory nerves in addition to motor nerves and can cause pain at high intensities. The degree of discomfort experienced by participants during stimulation will be quantified using the behavioral pain scale.¹⁸
- **Adverse Events** – All medical complications experienced by the study participants during the study will be assessed for severity and relationship to the study device and recorded.

8 Participant Selection

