12.6 Early Withdrawal Visit

In the case that the patient withdraws or is withdrawn from the protocol (see Section 14) before the end of the intervention period, and providing the patient consents, then the investigators will perform and record the participant's MEP, MIP, thickness of the abdominal wall muscles and diaphragm, CPF, resting breathing parameters and adverse events related to stimulation or otherwise.

If the participant is withdrawn from the study because they have successfully weaned from mechanical ventilation then the study researcher will also calculate and record the number of days taken to wean taken from the institution of mechanical ventilation.

13 Adverse Experience Reporting and Documentation

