14.1 Withdrawal of Participants from the Study

A participant may be withdrawn from study treatment at any time if the participant, the investigator, or the Sponsor feels that it is not in the participant's best interest to continue. The following is a list of possible reasons for study treatment discontinuation:

- Successful weaning from mechanical ventilation
- Participant withdrawal of consent
- Participant is not compliant with study procedures
- Adverse event that in the opinion of the investigator would be in the best interest of the participant to discontinue study treatment
- Protocol violation requiring discontinuation of study treatment
- Lost to follow-up
- Sponsor request for early termination of study
- Positive pregnancy test (females)

If a participant is withdrawn from treatment due to an adverse event, the participant will be followed and treated by the PI until the abnormal parameter or symptom has resolved or stabilized.

All participants who discontinue study treatment should come in for an early discontinuation visit as soon as possible.

All participants are free to withdraw from participation at any time, for any reason, specified or unspecified, and without prejudice. This will not affect the care they receive, now or in the future.

Reasonable attempts will be made by the investigator to provide a reason for participant withdrawals. The reason for the participant's withdrawal from the study will be specified in the participant's source documents.

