12.3 Replacement of Participants

While it is estimated that 24 is a suitable sample size for this study, the actual study sample size of 26 allows for a 10% drop out rate. Therefore, up to two participants who withdraw from the study will be replaced.

15 Protocol Violations

A protocol violation occurs when the participant, investigator, or Sponsor fails to adhere to significant protocol requirements affecting the inclusion, exclusion, participant safety and primary endpoint criteria.

Failure to comply with Good Clinical Practice (GCP) guidelines will also result in a protocol violation. The Sponsor will determine if a protocol violation will result in withdrawal of a participant.

When a protocol violation occurs, it will be discussed with the investigator and a Protocol Violation Form detailing the violation will be generated. This form will be signed by a Sponsor representative and the Investigator. A copy of the form will be filed in the site's regulatory binder and in the Sponsor's files.

16 Protocol Amendments

Amendments to the clinical investigation plan must be submitted to the Sponsor for review before submitting to the appropriate IRB for approval.

17 Statistical Methods and Considerations

Only participants who fulfil the protocol in terms of eligibility, interventions and outcome assessment will be included in the statistical analysis. Patient variables will be presented using means and standard deviations for continuous normally distributed variables, medians and interquartile ranges for continuous non-normally distributed variables, and proportions and absolute numbers for categorical variables.

Adverse event rates will be coded by body system and MedDra classification term. Adverse events will be tabulated by treatment group and will include the number of patients for whom the event occurred, the rate of occurrence, and the severity and relationship to study treatment.

Study results will first undergo descriptive level statistical analyses. For continuous variables, Two-way, Student's t-tests will then be carried out using unequal variances where the variables are normally distributed. Tests for normality will be carried out using the Shapiro-Wilk method. Variables that are not normal in distribution that also cannot be log transformed to a normal distribution curve will be analysed using the Mann-Whitney U test or other non-parametric methods to be determined based on actual data distributions.

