In the second level of analysis, we will quantify the magnitude to which abdominal NMES exhibits a protective effect. Crude and adjusted linear regression models will be carried out where the outcome variable is continuous and the covariates are normally distributed or categorical. Our prior experience with measures of respiratory function, which will be measured in this study, indicate that select covariates may need to be controlled for or otherwise do not always fit a normal distribution. Therefore, crude and adjusted generalized linear models are anticipated. These regression models will be carried out at the point of successful wean. All multiple regression covariates, linear or generalized, will be assessed for interaction, collinearity and confounding. For all unadjusted and adjusted multinomial models the overall model log likelihood ratio and Hosmer and Lameshow goodness-of-fit will be conducted to ensure models report significance and are not over fitted. Adjusted regression models will undergo sensitivity analysis and bootstrap analyses. Bootstrap analysis is a re-sampling strategy to estimate the population parameter of interest based on the observed, sample data.

The number of tries to successful wean will be quantified using Poisson regression. Crude and adjusted models will be carried out. Kaplan-Meier survival analysis will be carried out to quantify differences in the time to wean in the treatment abdominal NMES modality compared to the control. As the patients will be resident in hospital facilities, we do not anticipate significant methodological concerns with respect to censoring.

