17.1 Sample Size

This study is intended to be a pilot study that will be used to obtain initial data on the feasibility and safety of VentFree to assist in the process of ventilator weaning. The primary outcome of this study is the effect of abdominal NMES on respiratory muscle strength over time. There is currently no data in the literature to support a sample size calculation for this study. Given this constraint, in this pilot study a total of 24 participants was deemed adequate and is consistent with sample size recommendations in the literature.¹ Allowing for a 10% drop out rate, up to 26 participants will be recruited for this study. The data collected on the secondary endpoints will be used to determine the participants needed for a future randomized controlled trial of the device on weaning outcome.

18 Data Collection, Retention and Monitoring

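### Time off the ventilator has no common window or summary; if recording ends at weaning, as Section 12.6 and Appendix A read, observation length depends on the outcome and relapse or death before Day 45 is missed

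*Combined protocol and SAP*

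**What the plan says.** Section 7.2 (Secondary Outcome Measures): "The time spent breathing without MV support will be recorded on a daily basis throughout the study". No total, daily mean or other summary is named, and Section 17 does not mention this outcome.

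The documents differ on how long a weaned participant is observed:

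- Sections 2 and 6 give 45 days as a maximum. Stimulation ends at six weeks or at weaning, whichever is sooner.
- Section 6: "Evaluations will be performed at baseline, after three weeks of treatment and at the end of treatment". For a participant who weans early, the last evaluation therefore falls at weaning.
- Section 12.6 refers to a participant "withdrawn from the study because they have successfully weaned from mechanical ventilation".
- Appendix A marks this outcome in every column, including Early Withdrawal, and has no later column. The list of measurements in Section 12.6 itself omits it.
- Section 14.1 puts successful weaning under a different description: "The following is a list of possible reasons for study treatment discontinuation".
- Section 17, on the regression analyses: "These regression models will be carried out at the point of successful wean". That time differs between participants and does not exist for those who never wean. The same section expects no important censoring problem because participants are in hospital.

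Weaning success is 72 hours without support (Section 7.2). No section describes recording after that point.

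**The concern.** If Section 12.6 and Appendix A are followed, a participant who weans on Day 15 contributes about 15 days of data and one who never weans contributes 45. The better the outcome, the shorter the observation. Two things follow.

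First, the arms are compared over unequal periods whenever they differ in weaning. What that does to the result depends on a summary that the plan has not chosen.

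Second, a participant who returns to the ventilator or dies after the 72 hours but before Day 45 looks the same as one whose wean lasted. Nothing scheduled would pick this up, and later analysis cannot recover it.

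Section 17.1 gives this some weight beyond the pilot: "The data collected on the secondary endpoints will be used to determine the participants needed for a future randomized controlled trial". That applies only as far as this outcome is used for planning.

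**Working it through.** The documents give no figure for this outcome, so there is none to reproduce. All rates, hours and shapes below are assumptions. Results are given as active v control.

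**Two participants.** Each has 4 h/day off support before weaning; one weans on Day 15 (72 h completed) and one never weans.

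- Recording stops at weaning: 4 × 12 + 72 = 120 h v 4 × 45 = 180 h.
- Days 1 to 45: 120 + 24 × 30 = 840 h v 180 h.
- Mean per observed day: 120/15 = 8.0 v 4.0 h. The order is right, but the gap is 4.0 h/day against 840/45 − 4.0 = 14.7 h/day over the full window.

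**Two arms, main case.** Let T be the time to the start of the 72 h period, exponential, with control median 30 days and hazard ratio 2. Then λ = ln 2/30 = 0.0231 in control and 0.0462 in active. Pre-weaning hours are flat at 4 h/day.

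- Mean observation = 3 + (1 − e^(−42λ))/λ: 21.5 v 29.9 days.
- Mean of T capped at 45 = (1 − e^(−45λ))/λ: 18.94 v 27.98 days.
- Full-window hours = 24 × 45 − 20 × capped mean: 701 v 520 h, a difference of +181 h.
- Unrecorded hours if recording stops = 24 × (45 − mean observation): 563 v 363 h.
- Recorded total = 701 − 563 v 520 − 363: 138 v 158 h after rounding.

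Stopping at weaning thus removes 563 − 363 = 200 h from the arm difference, whatever the pre-weaning hours.

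**Other pre-weaning patterns, same weaning rates.** Rising hours, 24 × (t/T)^k, are included because Section 3.3 says that during daily breathing trials "the work of breathing accomplished by the ventilator is progressively reduced". The last column counts reversals over eight cells: control median 20, 30, 45 or 60 days, by hazard ratio 1.5 or 2.

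| Pre-weaning hours | Recorded total (h) | Full-window difference (h) | Recorded total reversed |
|---|---|---|---|
| 4 v 4 per day | 138 v 158 | +181 | 8 of 8 |
| 2 v 2 | 100 v 102 | +199 | 3 of 8 |
| 5 v 4 | 157 v 158 | +200 | 2 of 8 |
| 6 v 4 | 176 v 158 | +219 | 0 of 8 |
| rising, k = 1 | 271 v 306 | +166 | 4 of 8 |
| rising, k = 2 | 194 v 195 | +200 | 3 of 8 |
| rising, k = 4 | 136 v 122 | +215 | 1 of 8 |

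The total reverses in 21 of 56 combinations, some of them within a few hours of zero. The full-window difference favours active in all 56 (+77 to +219 h). The mean per observed day also favours active in all 56, but shows 39% to 84% of the full-window difference.

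**Return to ventilation.** Suppose a share of weaned participants resume ventilation a mean of 7 days (exponential) after the 72 h, then have 4 h/day off support. The mean days from return to Day 45, if all resumed, are 17.94 v 11.28 per participant. The full-window difference is 180.9 − 20 × (share in active × 17.94 − share in control × 11.28):

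- 40% v 20%: 82.5, about 83 h.
- 20% v 20%: about 154 h.
- 20% v 40%: about 199 h.

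The recorded 138 v 158 h are the same in all three.

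**The case against.** **The premise is a reading.** No section says outright that daily recording stops at weaning. Section 7.2's wording could be taken to run to Day 45, and Section 14.1 speaks of stopping treatment. This stands, which is why the point is conditional. Sections 6 and 12.6 and Appendix A still make stopping the more natural reading, and nothing schedules anything later.

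**The hours are not lost.** After a lasting wean they are 24 per day and follow from the weaning date. This also stands: most of the 563 v 363 h could be filled in. What cannot be filled in is whether the wean lasted and whether the participant survived.

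**Reversal needs a summary nobody chose.** A reader might infer that the plan will make a helpful device look harmful. The documents do not support that. Reversal needs a cumulative total, and even then occurs in a minority of the combinations. A mean per observed day is an equally natural summary and keeps the direction. With 12 per arm in the main case it reaches p < 0.05 (Welch) more often than the full window at 5 v 4 (36% v 33%) and 6 v 4 (56% v 40%), though less often at 4 v 4 (19% v 28%). Its denominator still depends on the outcome, and it too misses relapse.

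**Under no difference there is no bias.** If the arms share the same weaning, relapse and pre-weaning hours, stopping at weaning creates no expected arm difference. This is correct.

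**A fixed window largely repeats time to wean.** At equal flat hours it is a linear function of T up to Day 45. This stands, and is a reason to keep a pre-weaning summary beside it.

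**Conclusion.** The concern holds in conditional form. Sections 12.6 and 14.1 and Appendix A must be reconciled. If Section 12.6 and Appendix A govern, observation length depends on the outcome, and relapse or death between weaning and Day 45 is not captured. Under the assumed rates, a recorded total can understate, tie or, less often, reverse the arm difference (138 v 158 h recorded against 701 v 520 h in the main case). A mean per observed day keeps the direction but shrinks the difference.

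The weight is moderate. This is one secondary outcome in a pilot, and every rate here is an assumption. MIP/MEP and the separate weaning endpoints do not depend on it. It merits a change because the missing information can be collected only during the study. Section 17's restriction of the analysis population is a separate issue and is not part of this point.

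**What to change.** 1. Reconcile Sections 12.6 and 14.1 and Appendix A so that ending stimulation at weaning does not end data collection.
2. Record ventilator status and death from the chart to Day 45 for every participant who has not withdrawn consent to data use.
3. Define the outcome as hours free of ventilation over Days 1 to 45. Count 24 h/day after weaning, or the charted hours if ventilation resumes, and state how death is handled (for example, 0 h after death).
4. Report the number with unknown status by arm, with a simple best-case and worst-case analysis.
5. Show mean hours per day before weaning as a supporting result, so that progress before weaning is kept.

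The cost is protocol wording and a chart check in at most 26 participants, with no added visits. The result will overlap with time to wean. It may also be inconclusive if many have unknown status after discharge. In the main case, counting unknowns as ventilated in active and unsupported in control gives 181 − 0.20 × 563 = +68 h when 20% of weaned participants are unknown, and turns negative above 181/563 = 32%. The opposite assignment at 20% gives 181 + 0.20 × 363 = about +254 h.

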8.3 Exclusion Criteria

- Patients in whom NMES does not elicit a palpable contraction of the abdominal muscles.
- Participants with broken or irritated skin on the abdominal wall.

- History of neuromuscular disease
- Body mass index $> 35 \text{ kg/m}^2$
- Patients who are not medically stable
- Participants with a pacemaker
- Female participants who are pregnant
- Patients under the age of 18
- Patients who are expected to die within four weeks
- Patients who are unable to follow verbal instructions
- Patients with epilepsy
- Patients with an abdominal wall hernia
- Patients with anoxic encephalopathy
- Patients with history of, or active, substance abuse

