9.2 Blinding

The difference between active and placebo stimulation can be distinguished visually as active stimulation causes a tetanic muscle contraction whereas placebo stimulation causes a sub-tetanic muscle contraction. Therefore study personnel who apply the treatment to subject will not be blinded to study patients' treatment group assignment.

The following procedures will be used to ensure that patients are blinded to the treatment group that they have been assigned to:

- Study personnel will be instructed not to inform patients as to whether a tetanic or twitch contraction is the active or placebo treatment arm of the study.
- The appearance of the active and placebo stimulation devices will be identical.

In addition, all clinical staff not involved in the study and all study personnel who do not apply stimulation to patients will be blinded to the treatment group assignment of participants. This measure will help ensure that decisions to attempt weaning are unrelated to the study and are only based on clinical care.

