9.6 Device Administration

In both of the study arms (active and placebo stimulation), stimulation will be administered for thirty minutes, twice per day, 5 days per week for the shorter of six weeks or until the patient is weaned from mechanical ventilation by one of the two trained study researchers.

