9.6.3 Stimulation Session

At the start of the session the study researcher will apply 0.5 second bursts of stimulation starting from stimulation current of 5 mA and progressing in increments of 5 mA for each side of the abdomen until the participant reports that the sensation of stimulation is painful or until a maximum amplitude of 60 mA is reached. This upper limit in stimulation amplitude was based on the maximum tolerated stimulation amplitude found in our preliminary studies. A behavioral pain scale > 4 will be used to determine painful stimulation in patients who are unable to verbally communicate.¹⁸ The researcher will set the stimulation current to 90% of this maximum tolerable level (deemed acceptable in previous clinical studies performed by Liberate) and begin the session by turning on the exhalation synchronized stimulation mode of VentFree.

Throughout the session, heart rate, blood pressure, oxygen saturation and skin irritation will continuously be monitored. Every ten minutes, participants will be asked whether the intensity of abdominal wall muscle stimulation can be increased or should be decreased. During these 10-minute intervals, the investigator will quantify pain using the behavioral pain scale. If signs of distress develop, the investigator will stop the session and the attending physicians will provide immediate medical treatment, as appropriate. Criteria for distress include: a mean arterial blood pressure < 60 mmHg or > 110 mm Hg, heart rate < 40 beats per minute or > 130 beats per minute; respiratory rate > 40 breaths per minute, SpO₂ < 90%, score of > 4 on behavioral pain scale¹⁸, agitation or patient request to stop.

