11.13 Sensation of Stimulation

The participant's sensation of stimulation will be measured using the behavioral pain scale every five minutes while receiving electrical muscle stimulation.

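### Discomfort from stimulation is rated only by an observer who, as the sections read together, knows the arm; adding a participant self-rating at an existing check would be a cheap improvement

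*Combined protocol and SAP*

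**What the plan says.** Section 7.2 lists the sensation felt by the patient as a secondary outcome and names one instrument for it: "The degree of discomfort experienced by participants during stimulation will be quantified using the behavioral pain scale". Section 11.13 gives the procedure, again with that instrument alone: "sensation of stimulation will be measured using the behavioral pain scale every five minutes". It does not name the scorer. The schedule in Appendix A has a row for sensation at the stimulation visits but adds no other instrument.

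Section 9.6.3 describes the session itself. The participant is asked every ten minutes whether the intensity should change, and "During these 10-minute intervals, the investigator will quantify pain using the behavioral pain scale". Sessions are delivered "by one of the two trained study researchers" (Section 9.6). On blinding, Section 9.2 says that "study personnel who apply the treatment to subject will not be blinded", and that the two kinds of contraction can be told apart by eye. Participants are blinded. Section 8.3 excludes "Patients who are unable to follow verbal instructions".

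The synopsis lists sensation first among the efficacy evaluations and again among the secondary endpoints. Section 17 has no analysis specific to it, only generic between-group tests for continuous variables.

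**The concern.** The outcome is meant to capture what the participant feels, but the only recorded measure is an observer's judgement of behavior. The observer appears to be the person applying the stimulation, who knows whether it is active or placebo. Someone who expects active stimulation to be less comfortable, or who wants it to look tolerable, can shift the scores in either direction without intending to.

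At stake is whether a difference in discomfort between arms, or the absence of one, can be separated from what the rater expected. The same applies to the plain description of tolerability in the active arm, which matters because Section 17.1 gives feasibility and safety as the purpose of the pilot. A self-rating not collected during sessions cannot be recovered later.

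**Working it through.** The documents attach no figure to this outcome, so the main check is to set the sections side by side.

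**Step 1: who scores?** Section 11.13 is silent. Section 9.6.3 has the investigator score pain during the session. Section 9.6 says that one of two trained researchers gives the session. Section 9.2 leaves those who apply treatment unblinded. Study personnel who do not apply stimulation are blinded, but none of them is assigned to score this outcome. Even if one were, the visible contraction would reveal the arm at the bedside. An arm-aware scorer is therefore the natural reading, though it is inferred from three sections and not stated in one.

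**Step 2: what is collected from the participant?** Three things in Section 9.6.3 come from the participant: the report of pain that limits the current at session start, the answer about intensity every ten minutes, and a request to stop. Section 13.1 adds questioning about adverse events, and its mildest grade includes transient discomfort. None of these is a rating of discomfort recorded as the sensation outcome.

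**Step 3: could a self-rating be collected?** Section 8.3 requires that participants can follow spoken instructions, and a question is already put to them every ten minutes. Against this, Section 8.4 expects many to lack capacity to consent at inclusion, and Section 9.6.3 provides for patients who cannot communicate verbally. A self-rating is feasible for some participants. The documents do not say how many.

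**Step 4: how much could rater bias matter?** The documents give no size for it, so the following is an illustration on assumed values.

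- Inputs: n = 12 per arm (Section 6), or 13 per arm (synopsis); one summary score per participant; a two-sided 5% t-test; equal variances; no true difference.
- Assumed: a systematic scoring difference between arms of b standard deviations of that summary score.
- Formula: noncentrality = b × √(n/2), with 2n − 2 degrees of freedom. For n = 12 this is b × √6 = 2.449b with 22 degrees of freedom. For example, b = 0.5 gives 1.225.

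| Assumed bias b (SD) | False-positive rate, 12 per arm | False-positive rate, 13 per arm |
|---|---|---|
| 0 | 5% | 5% |
| 0.25 | 9% | 9% |
| 0.5 | 22% | 23% |
| 0.75 | 42% | 45% |
| 1.0 | 65% | 69% |

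Averaging many readings per participant reduces random error but leaves a systematic difference untouched.

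**Step 5: scoring interval.** Section 11.13 scores every five minutes and Section 9.6.3 every ten. In a 30-minute session that is 30/5 = 6 readings against 30/10 = 3, so the two sections do not describe the same data.

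**The case against.** The case for the plan is that one observer scale, usable in every participant, is a defensible choice in ventilated patients. It avoids mixing instruments in about 12 per arm, and it avoids participants switching instrument as they recover. A self-rating would not be free of bias either. Participants feel the stimulation, the current is set relative to tolerance in the active arm but fixed at 10 mA in the placebo arm (Sections 9.3.1 and 9.3.2), and the unblinded operator would ask the question. Some difference in discomfort is expected by design, and no comparison specific to sensation is planned. All of this stands. It argues for adding a self-rating alongside the behavioral scale and against replacing the scale.

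A reader might also infer several stronger points that the documents do not support:

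- *That Section 9.6.3 reserves the behavioral scale for non-communicators, so that 7.2 and 11.13 contradict it.* The sentence saying that a score above 4 "will be used to determine painful stimulation in patients who are unable to verbally communicate" concerns setting the current at session start. Scoring during the session, and the distress criterion that uses the scale, apply to everyone. On the choice of instrument the three sections agree.
- *That the participant's report is thrown away.* It sets the current, guides intensity, can end the session and can enter the adverse event record. What is missing is a self-rating as an outcome.
- *That most participants could self-rate.* Following instructions is an entry requirement, but no section gives a proportion able to rate discomfort repeatedly.
- *That the number of readings measures the problem.* Up to 60 sessions (2 × 5 × 6) at 3 to 6 readings gives 180 to 360 per participant. That is a maximum count of measurements and says nothing about the size of the bias.
- *That the scale is unsuitable in awake patients.* Only the title of the cited validation study points that way, and its content cannot be judged from these documents.

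**Conclusion.** The point holds as a cheap improvement. The sensation outcome has a single, observer-rated instrument, and the sections together indicate a rater who knows the arm. The blinded participant gives no rating that counts as an outcome, although a suitable moment to ask for one already exists in each session. Any between-arm comparison of discomfort, and the tolerability description, inherits that dependence on the rater.

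The size of the bias is unknown, and the range in the working depends wholly on the assumed values of b. The conclusion rests on two readings: that the person scoring under Section 11.13 is the operator described in Sections 9.6.3 and 9.6, and that the generic tests in Section 17 would be applied to this outcome. The consequence is modest, since this is one of ten secondary outcomes in a pilot and neither the primary endpoint nor the weaning outcomes depend on it.

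**What to change.** 1. In Sections 7.2 and 11.13, add a simple self-rating of discomfort, spoken or pointed, at the existing ten-minute intensity question, for every participant able to give one. Make it the main sensation measure in those participants.
2. Keep the behavioral pain scale in all participants, as the common measure and as the only one for those who cannot respond. Report the two separately.
3. Name the scorer in Section 11.13, and reconcile its five-minute interval with the ten-minute interval in Section 9.6.3.
4. Leave the session-stopping criteria unchanged.

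The cost is one question at a check that already takes place and one more CRF field, with no extra staff or procedure. Self-ratings will be missing for some participants, and who is missing may depend on how ill they are. Some bias will remain, because participants may sense their arm and the unblinded operator asks the question. Keeping the behavioral scale in everyone means that the small sample is not split between two instruments.
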